## **6.10. Appendix 9 Medications of Special Interest**

Not Applicable.

### **6.11. Appendix 10 Laboratory Toxicity Grading**

The grading scale use for lab assessments is based on ‘Common Terminology Criteria for Adverse Events (CTCAE) v5.0’.

If a laboratory value falls within the grading as specified below but also within the local laboratory normal limits, the value is considered to be normal and will be reset to grade 0.

Pre-baseline measurements will use the same grading ranges as applied to baseline measurements. In case a test has two sets of ranges – one for baseline normal and one for baseline abnormal, the one for baseline normal will be applied for all measurements taken pre-baseline and on baseline.

Text in gray italic in the table is present in the grading scale, but is not applied by Janssen when grading lab data.

| CTCAE Term                                      | Grade 1   | Grade 2  | Grade 3  | Grade 4  | Janssen implementation notes   |
|---|---|--|--|--|--|
| Blood and lymphatic system disorders     |   |  |  |  |  |
| Anemia  | Hemoglobin (Hgb)
<LLN - 10.0 g/dL;
<LLN - 6.2 mmol/L;
<LLN - 100 g/L             | Hemoglobin (Hgb)
<10.0 - 8.0 g/dL;
<6.2 - 4.9 mmol/L;
<100 - 80g/L                | Hemoglobin (Hgb) <8.0 g/dL;
<4.9 mmol/L;
<80 g/L;
transfusion indicated      | Life-threatening consequences;
urgent intervention indicated          | Clinical signs and symptoms are not taken into consideration for grading.  |
| Leukocytosis                                    | -   | -  | >100,000/mm  ;
>100 x 10  /L                                      | Clinical manifestations of leucostasis;
urgent intervention indicated | Clinical signs and symptoms are not taken into consideration for grading;
Added ranges in SI unit (x 10  /L)                  |
| Investigations                           |   |  |  |  |  |
| Activated partial thromboplastin time prolonged | >ULN - 1.5 x ULN  | >1.5 - 2.5 x ULN   | >2.5 x ULN;
bleeding   | -  | Clinical signs and symptoms are not taken into consideration for grading.  |
| Alanine aminotransferase increased              | >ULN - 3.0 x ULN if baseline was normal;
1.5 - 3.0 x baseline if baseline was abnormal | >3.0 - 5.0 x ULN if baseline was normal;
>3.0 - 5.0 x baseline if baseline was abnormal | >5.0 - 20.0 x ULN if baseline was normal;
>5.0 - 20.0 x baseline if baseline was abnormal | >20.0 x ULN if baseline was normal;
>20.0 x baseline if baseline was abnormal | Ranges defined for “abnormal baseline” are applied only if baseline > ULN. If baseline < LLN, then ranges for “normal baseline” are applied. |
| Alkaline phosphatase increased                  | >ULN - 2.5 x ULN if baseline was normal;
2.0 - 2.5 x baseline if baseline was abnormal | >2.5 - 5.0 x ULN if baseline was normal;
>2.5 - 5.0 x baseline if baseline was abnormal | >5.0 - 20.0 x ULN if baseline was normal;
>5.0 - 20.0 x baseline if baseline was abnormal | >20.0 x ULN if baseline was normal;
>20.0 x baseline if baseline was abnormal | Ranges defined for “abnormal baseline” are applied only if baseline > ULN. If baseline < LLN, then ranges for “normal baseline” are applied. |
| Aspartate aminotransferase increased            | >ULN - 3.0 x ULN if baseline was normal;
1.5 - 3.0 x baseline if baseline was abnormal | >3.0 - 5.0 x ULN if baseline was normal;
>3.0 - 5.0 x baseline if baseline was abnormal | >5.0 - 20.0 x ULN if baseline was normal;
>5.0 - 20.0 x baseline if baseline was abnormal | >20.0 x ULN if baseline was normal;
>20.0 x baseline if baseline was abnormal | Ranges defined for “abnormal baseline” are applied only if baseline > ULN. If baseline < LLN, then ranges for “normal baseline” are applied. |
| Blood bilirubin increased                       | >ULN - 1.5 x ULN if baseline was normal;  | >1.5 - 3.0 x ULN if baseline was normal;   | >3.0 - 10.0 x ULN if baseline was normal;  | >10.0 x ULN if baseline was normal;  | Ranges defined for “abnormal baseline” are   |

| CTCAE Term                | Grade 1   | Grade 2  | Grade 3  | Grade 4  | Janssen implementation notes  |
|---------------------------|---|--|--|--|---|
|                           | > 1.0 - 1.5 x baseline if baseline was abnormal   | >1.5 - 3.0 x baseline if baseline was abnormal   | >3.0 - 10.0 x baseline if baseline was abnormal  | >10.0 x baseline if baseline was abnormal  | applied only if baseline > ULN. If baseline < LLN, then ranges for “normal baseline” are applied.   |
| CD4 lymphocytes decreased | <LLN - 500/mm  ;
<LLN - 0.5 x 10  /L                           | <500 - 200/mm  ;
<0.5 - 0.2 x 10  /L                            | <200 - 50/mm  ;
<0.2 x 0.05 - 10e  /L                             | <50/mm  ;
<0.05 x 10e  /L                                 |   |
| Cholesterol high          | >ULN - 300 mg/dL;
>ULN - 7.75 mmol/L   | >300 - 400 mg/dL;
>7.75 - 10.34 mmol/L  | >400 - 500 mg/dL;
>10.34 - 12.92 mmol/L   | >500 mg/dL;
>12.92 mmol/L   |   |
| CPK increased             | >ULN - 2.5 x ULN  | >2.5 x ULN - 5 x ULN   | >5 x ULN - 10 x ULN  | >10 x ULN  |   |
| Creatinine increased      | Creatine Kinase
>ULN - 1.5 x ULN   | Creatine Kinase
>1.5 - 3.0 x baseline;
>1.5 - 3.0 x ULN                              | Creatine Kinase
>3.0 x baseline;
>3.0 - 6.0 x ULN                                      | Creatine Kinase
>6.0 x ULN  |   |
| Fibrinogen decreased      | <1.0 - 0.75 x LLN;
if abnormal, <25% decrease from baseline                            | <0.75 - 0.5 x LLN;
if abnormal, 25 - <50% decrease from baseline                        | <0.5 - 0.25 x LLN;
if abnormal, 50 - <75% decrease from baseline                          | <0.25 x LLN;
if abnormal, 75% decrease from baseline;
absolute value <50 mg/dL | Ranges defined for “abnormal” are applied only on values < LLN. Grade 0 will be assigned to values > ULN.   |
| GGT increased             | >ULN - 2.5 x ULN if baseline was normal;
2.0 - 2.5 x baseline if baseline was abnormal | >2.5 - 5.0 x ULN if baseline was normal;
>2.5 - 5.0 x baseline if baseline was abnormal | >5.0 - 20.0 x ULN if baseline was normal;
>5.0 - 20.0 x baseline if baseline was abnormal | >20.0 x ULN if baseline was normal;
>20.0 x baseline if baseline was abnormal     | Ranges defined for “abnormal baseline” are applied only if baseline > ULN. If baseline < LLN, then ranges for “normal baseline” are applied.              |
| Haptoglobin decreased     | <LLN  | -  | -  | -  |   |
| Hemoglobin increased      | Increase in >0 - 2 g/dL;
Increase in >0 - 20 g/L                                       | Increase in >2 - 4 g/dL;
Increase in >20 - 40 g/L                                       | Increase in >4 g/dL;
Increase in >40 g/L  | -  | The increase indicates the level of increase above normal (above ULN). Applied as, e.g. grade 1 (g/dL): >ULN – ULN+2 g/dL; Added ranges in SI unit (g/L). |
| INR increased             | >1.2 - 1.5;
>1 - 1.5 x baseline if on anticoagulation;
monitoring only indicated    | >1.5 - 2.5;
>1.5 - 2.5 x baseline if on anticoagulation;
dose adjustment indicated   | >2.5;
>2.5 x baseline if on anticoagulation;
bleeding                                  | -  | Concomitant therapy or clinical signs and symptoms are not taken into consideration for grading.  |

| CTCAE Term                                | Grade 1   | Grade 2  | Grade 3   | Grade 4   | Janssen implementation notes  |
|---|---|--|---|---|---|
| Lipase increased                          | >ULN - 1.5 x ULN  | >1.5 - 2.0 x ULN;
>2.0 - 5.0 x ULN and asymptomatic                           | >2.0 - 5.0 x ULN with signs or symptoms;
>5.0 x ULN and asymptomatic | >5.0 x ULN and with signs or symptoms                   | "Asymptomatic" ranges are not taken into consideration for grading, i.e. worst case grading is applied.         |
| Lymphocyte count decreased                | <LLN - 800/mm  ;
<LLN - 0.8 x 10  /L     | <800 - 500/mm  ;
<0.8 - 0.5 x 10  /L                  | <500 - 200/mm  ;
<0.5 - 0.2 x 10  /L         | <200/mm  ;
<0.2 x 10  /L     |   |
| Lymphocyte count increased                | -   | >4000/mm  - 20,000/mm  ;
>4 - 20 x 10  /L | >20,000/mm  ;
>20 x 10  /L                   | -   | Added ranges in SI unit (x 10  /L).   |
| Neutrophil count decreased                | <LLN - 1500/mm  ;
<LLN - 1.5 x 10  /L    | <1500 - 1000/mm  ;
<1.5 - 1.0 x 10  /L                | <1000 - 500/mm  ;
<1.0 - 0.5 x 10  /L        | <500/mm  ;
<0.5 x 10  /L     | Both Neutrophils and segmented neutrophils are graded using these criteria.                                     |
| Platelet count decreased                  | <LLN - 75,000/mm  ;
<LLN - 75.0 x 10  /L | <75,000 - 50,000/mm  ;
<75.0 - 50.0 x 10  /L          | <50,000 - 25,000/mm  ;
<50.0 - 25.0 x 10  /L | <25,000/mm  ;
<25.0 x 10  /L |   |
| Serum amylase increased                   | >ULN - 1.5 x ULN  | >1.5 - 2.0 x ULN;
>2.0 - 5.0 x ULN and asymptomatic                           | >2.0 - 5.0 x ULN with signs or symptoms;
>5.0 x ULN and asymptomatic | >5.0 x ULN and with signs or symptoms                   | "Asymptomatic" ranges are not taken into consideration for grading, i.e. worst case grading is applied.         |
| White blood cell decreased                | <LLN - 3000/mm  ;
<LLN - 3.0 x 10  /L    | <3000 - 2000/mm  ; <3.0 - 2.0 x 10  /L                   | <2000 - 1000/mm  ; <2.0 - 1.0 x 10  /L          | <1000/mm  ;
<1.0 x 10  /L    |   |
| Metabolism and nutrition disorders |   |  |   |   |   |
| Acidosis                                  | pH <normal, but ≥7.3  | -  | pH <7.3   | Life-threatening consequences                           | pH <normal is implemented as pH <LLN. Clinical signs and symptoms are not taken into consideration for grading. |
| Alkalosis                                 | pH >normal, but ≤7.5  | -  | pH >7.5   | Life-threatening consequences                           | pH >normal is implemented as pH >ULN. Clinical signs and symptoms are not taken into consideration for grading. |

| CTCAE Term           | Grade 1  | Grade 2  | Grade 3  | Grade 4  | Janssen implementation notes  |
|----------------------|--|--|--|--|---|
| Hypercalcemia        | Corrected serum calcium of >ULN - 11.5 mg/dL;
>ULN - 2.9 mmol/L;

Ionized calcium >ULN - 1.5 mmol/L | Corrected serum calcium of >11.5 - 12.5 mg/dL;
>2.9 - 3.1 mmol/L;

Ionized calcium >1.5 - 1.6 mmol/L;

symptomatic | Corrected serum calcium of >12.5 - 13.5 mg/dL;
>3.1 - 3.4 mmol/L;

Ionized calcium >1.6 - 1.8 mmol/L;

hospitalization indicated | Corrected serum calcium of >13.5 mg/dL; >3.4 mmol/L;

Ionized calcium >1.8 mmol/L;

life-threatening consequences | Clinical signs and symptoms are not taken into consideration for grading. |
| Hyperkalemia         | Potassium >ULN - 5.5 mmol/L  | Potassium >5.5 - 6.0 mmol/L;

intervention initiated  | Potassium >6.0 - 7.0 mmol/L;

hospitalization indicated   | Potassium >7.0 mmol/L;

life-threatening consequences   | Clinical signs and symptoms are not taken into consideration for grading. |
| Hypermagnesemia      | Magnesium >ULN - 3.0 mg/dL;
>ULN - 1.23 mmol/L  | -  | Magnesium >3.0 - 8.0 mg/dL;
>1.23 - 3.30 mmol/L   | Magnesium >8.0 mg/dL;
>3.30 mmol/L;

life-threatening consequences   | Clinical signs and symptoms are not taken into consideration for grading. |
| Hypernatremia        | Sodium >ULN - 150 mmol/L   | Sodium >150 - 155 mmol/L;

intervention initiated   | Sodium >155 - 160 mmol/L;

hospitalization indicated  | Sodium >160 mmol/L;

life-threatening consequences  | Clinical signs and symptoms are not taken into consideration for grading. |
| Hypertriglyceridemia | Triglycerides 150 mg/dL - 300 mg/dL;
1.71 mmol/L - 3.42 mmol/L  | Triglycerides >300 mg/dL - 500 mg/dL;
>3.42 mmol/L - 5.7 mmol/L   | Triglycerides >500 mg/dL - 1000 mg/dL;
>5.7 mmol/L - 11.4 mmol/L  | Triglycerides >1000 mg/dL;
>11.4 mmol/L;

life-threatening consequences  | Clinical signs and symptoms are not taken into consideration for grading. |
| Hypoalbuminemia      | Albumin <LLN - 3 g/dL;
<LLN - 30 g/L  | Albumin <3 - 2 g/dL;
<30 - 20 g/L   | Albumin <2 g/dL;
<20 g/L  | Life-threatening consequences;
urgent intervention indicated  | Clinical signs and symptoms are not taken into consideration for grading. |
| Hypocalcemia         | Corrected serum calcium of <LLN - 8.0 mg/dL;
<LLN - 2.0 mmol/L;

Ionized calcium <LLN - 1.0 mmol/L  | Corrected serum calcium of <8.0 - 7.0 mg/dL; <2.0 - 1.75 mmol/L;

Ionized calcium <1.0 - 0.9 mmol/L;                               | Corrected serum calcium of <7.0 - 6.0 mg/dL;
<1.75 - 1.5 mmol/L;

Ionized calcium <0.9 - 0.8 mmol/L;  | Corrected serum calcium of <6.0 mg/dL; <1.5 mmol/L;

Ionized calcium <0.8 mmol/L;  | Clinical signs and symptoms are not taken into consideration for grading. |

| CTCAE Term                         | Grade 1   | Grade 2  | Grade 3   | Grade 4   | Janssen implementation notes  |
|------------------------------------|---|--|---|---|---|
|                                    |   | symptomatic   | hospitalization indicated  | life-threatening consequences  |   |
| Hypoglycemia                       | Glucose
<LLN - 55 mg/dL;
<LLN - 3.0 mmol/L  | Glucose
<55 - 40 mg/dL;
<3.0 - 2.2 mmol/L  | Glucose
<40 - 30 mg/dL;
<2.2 - 1.7 mmol/L   | Glucose
<30 mg/dL;
<1.7 mmol/L;
life-threatening consequences;
seizures | Clinical signs and symptoms are not taken into consideration for grading. Urine glucose is not graded.  |
| Hypokalemia                        | Potassium <LLN - 3.0 mmol/L   | Symptomatic with Potassium <LLN - 3.0 mmol/L;
intervention indicated | Potassium <3.0 - 2.5 mmol/L;
hospitalization indicated  | Potassium <2.5 mmol/L;
life-threatening consequences                                    | “Symptomatic” ranges are applied for grade 2, grade 1 not assigned, i.e. worst case applied. Clinical signs and symptoms are not taken into consideration for grading of grade 3 and 4.   |
| Hypomagnesemia                     | Magnesium
<LLN - 1.2 mg/dL;
<LLN - 0.5 mmol/L   | Magnesium
<1.2 - 0.9 mg/dL;
<0.5 - 0.4 mmol/L                                      | Magnesium
<0.9 - 0.7 mg/dL;
<0.4 - 0.3 mmol/L   | Magnesium
<0.7 mg/dL;
<0.3 mmol/L;
life-threatening consequences                  | Clinical signs and symptoms are not taken into consideration for grading.   |
| Hyponatremia                       | Sodium <LLN - 130 mmol/L  | Sodium 125-129 mmol/L and asymptomatic  | Sodium 125-129 mmol/L symptomatic;
120-124 mmol/L regardless of symptoms

Sodium <130-120 mmol/L | Sodium <120 mmol/L;
life-threatening consequences                                       | Clinical signs and symptoms are not taken into consideration for grading.
Worst case (“<130-120 mmol/L” for grade 3 added by Janssen) is applied across grade 2/3 ranges: 120-129 mol/L assigned to grade 3, grade 2 not used. |
| Renal and urinary disorders |   |  |   |   |   |
| Proteinuria                        | 1+ proteinuria;
urinary protein ≥ULN -
<1.0 g/24 hrs;
urinary protein ≥ULN -
<1000 mg/day | Adult:
2+ and 3+ proteinuria;
urinary protein 1.0 - <3.5 g/24 hrs;          | Adult:
4+ proteinuria;
urinary protein ≥3.5 g/24 hrs;  | -   | In case both 24-h urine collection and dipstick are collected, then worst case is taken, as opposed to having 24-h urine  |

| CTCAE Term | Grade 1 | Grade 2  | Grade 3  | Grade 4 | Janssen implementation notes   |
|------------|---------|--|--|---------|--|
|            |         | urinary protein 1000 - <3500 mg/day

Pediatric:
Urine P/C (Protein/Creatinine) ratio 0.5 - 1.9;
Urine P/C (Protein/Creatinine) 56.5 – 214.7 g/mol | urinary protein $\geq$ 3500 mg/day;

Pediatric:
Urine P/C (Protein/Creatinine) ratio $>1.9$ ;
Urine P/C (Protein/Creatinine) $>214.7$ g/mol |         | collection take precedence over dipstick. Added ranges in SI unit for urinary protein (mg/day) and for urine P/C (g/mol). Pediatric grading is applied to age range [0-18]. Adult grading is applied for ages [ $>18$ ]. |

\* Grade 0 is assigned to a lab assessment when the lab test is described in the table, but the lab value is not assigned a grade 1 or higher.

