### **Screening Laboratory Test Parameters**

18. have screening laboratory test results within the following parameters. If one or more of the laboratory parameters is out of range, a single retest of laboratory values is permitted:
  - a. Hemoglobin  $\geq 10$  g/dL (SI:  $\geq 100$  g/L)
  - b. White blood cells  $\geq 3.5 \times 10^3/\mu\text{L}$  (SI:  $\geq 3.5$  GI/L)
  - c. Neutrophils  $\geq 1.5 \times 10^3/\mu\text{L}$  (SI:  $\geq 1.5$  GI/L)
  - d. Platelets  $\geq 100 \times 10^3/\mu\text{L}$  (SI:  $\geq 100$  GI/L)
  - e. Estimated glomerular filtration rate (eGFR)  $\geq 60$  mL/min/1.73 m^2

- f. Aspartate aminotransferase  $\leq 2 \times$  upper limit of normal (ULN)
- g. Alanine aminotransferase  $\leq 2 \times$  ULN
- h. Alkaline phosphatase  $\leq 2 \times$  ULN

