#### **Clinical Laboratory Tests**

Laboratory data will be summarized by type of laboratory test (eg, hematology, clinical chemistry). Selected laboratory parameters will be summarized by treatment groups. Common Terminology Criteria (CTC) and ULN will be used to identify abnormal laboratory test results, and the incidence and severity of abnormal laboratory parameters (hematology and chemistry) will be summarized by treatment group. In addition, a listing of participants with Grade 2 or higher laboratory test results (based on the CTC criteria and ULN) will also be provided.

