#### Phase 2 Liver Chemistry Stopping Criteria and Increased Monitoring Algorithm (no preexisting liver disease)

### 10.6.2. Follow-Up Assessments

#### 10.6.2.1. Phase 2 Liver Chemistry Stopping Criteria and Follow-up Assessments

Phase 2 liver chemistry stopping criteria are designed to assure participant safety and to evaluate liver event etiology.

Liver Chemistry Stopping Criteria	
ALT/AST-absolute	ALT or AST $\geq 5 \times \text{ULN}$
ALT/AST-Increase	
If cannot monitor: ALT or AST <math>\geq 3 \times \text{ULN}</math> and cannot be monitored weekly for 4 weeks
 
Or if able to monitor: ALT or AST <math>\geq 3 \times \text{ULN}</math> persists for <math>\geq 4</math> weeks

Total bilirubin	ALT or AST $\geq 3 \times \text{ULN}$ and total bilirubin $\geq 2 \times \text{ULN}$ (or at least a doubling of direct bilirubin in known Gilbert's syndrome)
INR^2	ALT $\geq 3 \times \text{ULN}$ and international normalized ratio (INR) $> 1.5$ , if INR measured
Symptomatic	ALT or AST $\geq 3 \times \text{ULN}$ associated with symptoms (new or worsening) believed to be related to liver injury or hypersensitivity
Suggested Actions, Monitoring and Follow-up Assessments	
Actions	Follow-up Assessments

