## 5. STATISTICAL ANALYSES

### 5.1. General Considerations

Unless specified otherwise, efficacy data summaries will be provided by intervention group for FAS. Data primarily will be summarized using descriptive statistics. Continuous variables will be summarized using the number of observations, mean, SD, median, interquartile range, minimum and maximum, as appropriate. Categorical values will be summarized using the number of observations and percentages as appropriate. In addition, graphical data displays (eg, line plots) and participant listings may also be used to summarize/present the data.

For binary response efficacy endpoints, comparisons between each of the JNJ-77242113 CCI groups versus placebo will be performed using a Cochran-Mantel-Haenszel (CMH) test stratified by the baseline weight ( $\leq 90$  kg,  $>90$  kg). For continuous efficacy endpoints, treatment comparisons will be performed using a Mixed-Effect Model Repeated Measure (MMRM) model. The MMRM model will have factors for treatment group, baseline weight ( $\leq 90$  kg,  $>90$  kg), baseline value for the corresponding efficacy endpoint, visit, and treatment group by visit interaction. An unrestricted (UN) variance-covariance matrix for repeated measures within a participant will be used. If the model with unstructured covariance structure does not converge, alternative covariance structures

will be considered in the following order, with the first structure that converges being used in the analysis: heterogeneous Toeplitz, standard Toeplitz, and autoregressive of order 1.

The Least Square mean (LSmean) estimates and their corresponding 90% confidence interval (CI) will be provided at each time point. In addition, the estimates of LSmean difference and 90% CIs between the JNJ-77242113 groups and placebo will be provided.

In general, all statistical tests will be performed at a 2-sided significance level of  $\alpha=0.10$ . Nominal p-values will be reported. No multiplicity adjustment is planned for this phase 2a proof-of-concept study.

The baseline measurement is defined as the closest measurement taken prior to or at the time of the first study agent administration date unless otherwise specified.

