### 5.6.3. Additional Safety Assessments

#### 5.6.3.1. Clinical Laboratory Tests

Clinical laboratory tests will be displayed for the participants included in the safety analysis set.

Descriptive statistics and graphical displays will be presented for selected chemistry and hematology laboratory tests at scheduled time points.

Change from baseline through Week 20 will be summarized for chemistry, and hematology tests and displayed by intervention group. Box plots of laboratory measurements and change from baseline will be provided for the selected laboratory measurement.

- **Hematology** will include but are not limited to the following: Basophils, Eosinophils, Hemoglobin, Lymphocytes, Monocytes, Neutrophils, Platelets, WBC, CRP and ESR.
- **Chemistry** will include but are not limited to the following: ALT, AST, Albumin, Alkaline Phosphatase, Bicarbonate (CO2), Calcium, Chloride, Creatinine, GGT, Glucose, Potassium, SGOT, SGPT, Sodium, Total Bilirubin, Total Protein, Urea Nitrogen.

Applicable laboratory results will be graded according to National Cancer Institute's Common Terminology Criteria for Adverse Events (NCI-CTCAE). The proportion of participants with post-baseline values by maximum toxicity grade for clinical laboratory tests will be summarized by study intervention group. Participants with toxicity grades  $\geq 2$  will be listed.

In addition, for selected laboratory parameters, LLN and ULN will also be used to identify abnormal laboratory test results, and the incidence and severity of abnormal laboratory parameters (hematology and chemistry) will be summarized by treatment group. Participants with maximum post-baseline elevated liver function tests through Week 20 relative to ULN will be summarized in categories as shown below will be provided.:

- $> 1$  to  $\leq 3$  x ULN
- $> 3$  to  $\leq 5$  x ULN
- $> 5$  to  $\leq 10$  x ULN
- $> 10$  to  $\leq 20$  x ULN

- $> 20 \times \text{ULN}$

In addition, Summary of potential Hy's Law case (ALT or AST  $\geq 3 \times \text{ULN}$  and total bilirubin  $\geq 2 \times \text{ULN}$  or INR  $> 1.5$ ) through Week 20 will also be provided.

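### With a baseline of 1.67 to 2.0 x ULN, an ALT or AST at the protocol's 5 x ULN stopping limit can be Grade 1 and so absent from the SAP's only laboratory listing

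*SAP*

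**What the plan says.** - **Entry.** Protocol 5.1, criterion 18, requires participants to "have screening laboratory test results within the following parameters", among them "Alanine aminotransferase $\leq 2 \times$ ULN". AST has the same ceiling. A raised enzyme level at entry is therefore allowed.
- **Baseline.** SAP 5.1: "The baseline measurement is defined as the closest measurement taken prior to or at the time of the first study agent administration date".
- **Grading.** In SAP 6.11 (Appendix 10), ALT and AST have two sets of ranges. If baseline is not above ULN, the cut-offs are multiples of ULN. If baseline is above ULN, they are multiples of baseline: Grade 1 is "1.5 - 3.0 x baseline if baseline was abnormal" and Grade 2 is ">3.0 - 5.0 x baseline if baseline was abnormal".
- **Listing.** SAP 5.6.3.1 lists participants with toxicity grade 2 or higher and states no ULN criterion for that listing. Protocol 9.4.5 (Clinical Laboratory Tests) planned "a listing of participants with Grade 2 or higher laboratory test results (based on the CTC criteria and ULN" (the parenthesis closes there). SAP Appendix 2, which records changes from the protocol's planned analyses, is marked not applicable.
- **Summaries.** SAP 5.6.3.1 also says: "Participants with maximum post-baseline elevated liver function tests through Week 20 relative to ULN will be summarized in categories". The bands are >1 to <=3, >3 to <=5, >5 to <=10, >10 to <=20 and >20 x ULN. A separate summary covers potential Hy's Law cases.
- **Stopping limits.** Protocol 10.6.2.1: "Phase 2 liver chemistry stopping criteria are designed to assure participant safety and to evaluate liver event etiology". The absolute criterion is ALT or AST >=5 x ULN, whatever the baseline. Other criteria start at >=3 x ULN combined with persistence, inability to monitor, bilirubin, INR (ALT only) or symptoms. Section 10.6.1.1 makes discontinuation of study intervention mandatory when a criterion is met.

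**The concern.** The protocol's liver limits are fixed multiples of ULN. The SAP's only laboratory listing is triggered by a grade that, for a participant who enters with raised enzymes, is a multiple of that participant's own baseline. The two scales can disagree for the participants in whom a further rise most needs individual review. A value that obliges the site to stop study intervention can carry the lowest abnormal grade and fall below the listing threshold.

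A reviewer who uses the laboratory listing to check the stopping criteria would not see that value. This is an early study with a target of 80 participants and one of the first two of this compound in psoriasis, so a single liver case deserves to be visible with its numbers.

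**Working it through.** The plan gives no figure to reproduce here. The check applies the SAP 6.11 ranges to the protocol's limits.

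**Notation.** Baseline is b x ULN and the post-baseline value is v x ULN. For b > 1, v is Grade 1 if 1.5 <= v/b <= 3.0 and Grade 2 if 3.0 < v/b <= 5.0. For b <= 1, v is Grade 1 up to 3.0 and Grade 2 above 3.0 up to 5.0.

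**Step 1: which baselines make 5.0 x ULN Grade 1?** The condition is 5.0/b <= 3.0, so b >= 5/3 = 1.67. With the entry ceiling of 2.0, the affected baselines are 1.67 to 2.0 x ULN.

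| Baseline b (x ULN) | Top of Grade 1 (x ULN) | 5.0 x ULN as a multiple of baseline | Grade at 5.0 x ULN | On the grade >=2 listing? |
|---|---|---|---|---|
| 1.0 or below | 3.0 | graded on ULN | 2 | yes |
| 1.2 | 3.6 | 4.17 | 2 | yes |
| 1.5 | 4.5 | 3.33 | 2 | yes |
| 5/3 | 5.0 | 3.00 | 1 | no |
| 1.8 | 5.4 | 2.78 | 1 | no |
| 2.0 | 6.0 | 2.50 | 1 | no |

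At b = 2.0, every value from 5.0 to 6.0 x ULN meets the absolute stopping limit and is Grade 1 (5.5/2.0 = 2.75; 6.0/2.0 = 3.0). From a normal baseline, 5.0 x ULN is Grade 2 and 6.0 x ULN is Grade 3.

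**Step 2: the combined criteria.** For any b above 1, values from 3.0 to 3b x ULN are Grade 1 at most. At b = 1.5, a value of 4.0 x ULN is 4.0/1.5 = 2.67 x baseline, so Grade 1. If it persists for 4 weeks it meets a stopping criterion and is still not on the listing. This is why the repair starts at 3 x ULN.

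**Step 3: Week 0 baseline above the entry ceiling.** The ceiling applies to the screening test, while baseline is normally the Week 0 sample. For assumed baselines of 2.5 and 3.4 x ULN, 5.0 x ULN is 2.0 x baseline (Grade 1) and 1.47 x baseline (Grade 0). This would add to the affected set, but it is not needed for the conclusion.

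**Step 4: the ULN table.** Its bands ignore baseline. Exactly 3.0 x ULN falls in >1 to <=3 and exactly 5.0 x ULN in >3 to <=5, while the protocol's limits are >=3 and >=5. All other ALT/AST values fall on the correct side; for example, 5.01 to 6.0 x ULN is in >5 to <=10.

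**Step 5: how many.** The documents give no rates. Assume that 10% of 80 (8 participants) enter above ULN and that 2% to 5% of those exceed 3 x ULN: 8 x 0.02 = 0.16 and 8 x 0.05 = 0.40. The absolute-limit case needs b >= 1.67 and a value between 5 x ULN and 3 x baseline, a narrower set, so its expected number is smaller still.

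**The case against.** The strongest reply is that the case is already caught elsewhere. A participant at the absolute limit must be discontinued and reported to the sponsor within 24 hours (Protocol 10.6). SAP 5.2 lists everyone who discontinued study intervention, and SAP 5.6.2 lists adverse events leading to discontinuation if one is recorded. The baseline-independent table counts values above 5 x ULN, and the Hy's Law summary already uses >=3 x ULN for ALT or AST and >=2 x ULN for bilirubin. The grading follows CTCAE v5.0 by declaration, so it is a choice and not a transcription error. Protocol 5.2 also excludes fatty liver disease, steatohepatitis and severe or uncontrolled liver disturbance, which makes raised baselines less common.

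All of this stands, and it rules out several stronger readings:

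- A reader might infer that the participant disappears from every listing. The documents do not support this. The gap is in the laboratory listing; the discontinuation listings remain, but they are not specified to show enzyme values.
- A reader might infer that the ULN table is unusable against the protocol's ALT/AST limits. It differs from them only at exact equality.
- A reader might want separate bilirubin and ALP listings or bands at 2 x ULN. Bilirubin >=2 x ULN is a stopping limit only jointly with ALT or AST, and that combination is already summarised. From a normal baseline it is also Grade 2 and listed. ALP at 2 x ULN is an entry limit and, as <2 x ULN, a qualifier for possible Hy's Law; it is not a stopping limit.

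It can also be argued that the wording in protocol 9.4.5 is met by CTC ranges that are themselves ULN multiples. That works for a normal baseline. For a raised baseline, ULN only selects which ALT/AST ranges apply and sets none of the cut-offs.

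**Conclusion.** The point holds as a narrow reporting gap. For eligible baselines of 1.67 to 2.0 x ULN, an ALT or AST at the protocol's absolute stopping limit can be Grade 1 and so missing from the only laboratory listing. The SAP's listing rule omits the ULN element named in protocol 9.4.5, and no change is declared.

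Importance is low. Well below one participant is expected under the assumed rates, which come from outside the documents. No efficacy result, stopping decision or Hy's Law summary is affected. The grade arithmetic itself rests only on the SAP ranges and the protocol limits.

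**What to change.** In SAP 5.6.3.1:

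1. Keep the CTCAE grading and the grade >=2 listing as they are.
2. Also list every participant with a post-baseline ALT or AST >=3 x ULN, whatever the grade, showing the baseline value and the concurrent bilirubin and ALP.
3. Set the ALT/AST category bounds at >=3 and >=5 x ULN, to match the protocol's own limits. The bounds at 10 and 20 x ULN can stay.

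After the change, the case with b = 2.0 and v = 5.0 moves from Grade 1, unlisted and in >3 to <=5, to listed and in the band that starts at >=5. Its grade is unchanged. A value of exactly 3.0 x ULN moves into the band that starts at >=3.

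The cost is a few words in the SAP, one listing filter and a slightly longer listing. No clinical rule changes.
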